7.2 Dose Halting Rules

The following sections define halting rules, which are pre-defined criteria that halt the conduct of the study (either a single cohort or the entire study). These rules are to ensure the safety of study subjects. The following criteria including grading scales to be used in this study are based on the CBER (FDA) Guidance for Industry “Toxicity Grading Scale of Healthy Adult and Adolescent Volunteers Enrolled in Preventative Vaccine Clinical Trials”.⁴ Specific safety terms and reaction grading criteria are defined in Section 9.15.

Dosing of all subjects in a cohort shall be halted for any event suggesting that there is a significant safety risk to other subjects of the cohort, or when a clinically significant pattern of toxicity is apparent in more than one subject. The following events will result in a temporary halt of dosing within that cohort:

- The occurrence of a SAE assessed, as possibly or probably related to the study vaccine;
- The occurrence of a clinically significant unsolicited severe AE (Grade 3 AE), including vital signs, and/or a laboratory abnormality assessed as possibly or probably related to the study vaccine in ≥ 2 subjects in the same cohort; or
- 2 or more of the subjects enrolled in each cohort experience a severe (Grade 3):

- Allergic reaction (e.g., hives, angioedema, allergic asthma, systemic anaphylaxis) that is assessed as related to study vaccine; or
- Vaccine-related injection site ulceration, abscess, or necrosis.

If any of the above halting rules are met, dosing will be suspended for all subjects in that cohort, while continuation of other cohorts at lower or equivalent dose levels will be evaluated on a case-by-case basis. The SRC will review details of the event(s) and/or additional data. If, after further review of the data, the SRC determines that no halting rules have been met e.g., AE determined to be unrelated to the study vaccine, then dosing of the cohort may resume.

The Sponsor or the Investigator (after consultation with the Sponsor) has the right to discontinue the study at any time. If the clinical study is prematurely terminated, the clinical site must promptly inform the study subjects and must ensure that appropriate treatment and follow-up for the subjects is made available. The Sponsor must notify the HREC should the study be discontinued.

8. Study Population

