5.2.2 Choice of the Dose

The planned SARS-CoV-2 Sclamp doses to be investigated in this FIH study are 5, 15, and 45 mcg. The study is designed as a dose escalation study with the safety of the 5 mcg dose to be evaluated by a Safety Review Committee prior to escalation to the 15 mcg, and similarly prior to escalation to the 45 mcg dose.

The starting dose of 5 mcg and highest dose of 45 mcg SARS-CoV-2 Sclamp are based on comparable viral subunit vaccines approved for use as outlined below and in the IB:

RECOMBIVAX HB[®] (Hepatitis B vaccine, recombinant, Adjuvanted)

- Paediatric and adolescent formulation: Contains 5 mcg antigen + 0.25mg aluminium (provided as amorphous aluminium hydroxyphosphate) – Recommended 3 doses of 0.5 mL given by IM injection on a 0-, 1-, and 6-month schedule.
- Adult (≥ 20 years) formulation: Contains 10 mcg antigen + 0.5mg aluminium (provided as amorphous aluminium hydroxyphosphate) - Recommended 3 doses of 0.5 mL given by IM injection on a 0-, 1-, and 6-month schedule.
- HEPLISAV-B[®] (Hepatitis B vaccine, recombinant, Adjuvanted)
 - Adult (≥ 18 years): Contains 20 mcg antigen + 3mg CPG-1018 - Recommended 2 doses of 0.5 mL given by IM injection on a 0- and 1-month schedule.
- GARDASIL^{®9} (Human Papillomavirus 9-valent vaccine, recombinant, Adjuvanted)
 - Children (>9 years) and adult: Contains 20 - 60 mcg antigen per strain for each of nine strains + 0.5mg aluminium (provided as amorphous aluminium hydroxyphosphate) – Recommended 3 doses of 0.5 mL given by IM injection on a 0-, 2-, and 6-month schedule.
- SHINGRIX[®] (Zoster Vaccine Recombinant, Adjuvanted),
 - Adult (>50 years): Reconstituted vaccine contains 50 mcg antigen + AS01b adjuvant – Recommended 2 doses of 0.5 mL given by IM injection on a 0-, 2-, and 6-month schedule.

Additionally, the choice of dose is supported by previous experience evaluating MC vaccines. Immunopathology and animal protection of SARS-CoV-2 Sclamp have investigated doses of 5 mcg per dose in mice indicating that a neutralising immune response was induced by the SARS-CoV-2 Sclamp vaccine. Further pre-clinical examinations in hamsters (also at 5 mcg per dose) and ferrets (at 20 mcg per dose), are ongoing, the results of which will be included in the SARS-CoV-2 Sclamp Investigator's Brochure.

Objectives and Endpoints

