The study will evaluate a single formulation of SARS-CoV-2 Sclamp protein subunit vaccine administered as a single dose or two doses of varying vaccine antigen concentrations in distinct cohorts.

Four treatments (A, B, C, and D) will be administered to subjects.

This study will consist of 6 cohorts: 2 cohorts of a lower dose (Treatment A), 2 cohorts of an intermediate dose (Treatment B), 1 cohort of a higher dose (Treatment C)(Part 2 only), and 1 cohort of a higher dose, examining both a two dose regimen (Treatment C) and a single dose vaccination regimen (Treatment D) (Part 1 only).

Cohorts 1,2 and 3 will include subjects aged ≥ 18 - ≤ 55 years of age and cohorts 4, 5 and 6 will include subjects aged 56 years and older. Cohorts 4, 5 and 6 will include an approximately equal number of subjects aged ≥ 56 - ≤ 65 years of age, and ≥ 66 years and over.

Part 1: Cohort 1 will include 32 subjects; of these 8 will receive placebo, and 24 subjects will receive Treatment A. Cohort 2 will include 32 subjects; of these 8 will receive placebo, and 24 subjects will receive Treatment B. Cohort 3 will include 56 subjects; of these 8 will receive placebo, 24 subjects will receive Treatment C, and 24 subjects will receive Treatment D.

Part 2: Cohort 4 will include 32 subjects; of these 8 will receive placebo, and 24 subjects will receive Treatment A. Cohort 5 will include 32 subjects; of these 8 will receive placebo, and

24 subjects will receive Treatment B. Cohort 6 will include 32 subjects; of these 8 will receive placebo, and 24 subjects will receive Treatment C.

Treatment	Dose regimen
Treatment A (Cohorts 1 & 4)	SARS-CoV-2 Sclamp vaccine 1 x 5 mcg, or placebo, administered in a two dose regimen, at least 28 days apart
Treatment B (Cohorts 2 & 5)	SARS-CoV-2 Sclamp vaccine 1 x 15 mcg, or placebo, administered in a two dose regimen, at least 28 days apart
Treatment C (Cohorts 3 & 6)	SARS-CoV-2 Sclamp vaccine 1 x 45 mcg, or placebo, administered in a two dose regiment, at least 28 days apart
Treatment D (Cohort 3 only)	SARS-CoV-2 Sclamp vaccine 1 x 45 mcg, or placebo, administered as a single dose, followed by placebo as the second dose at least 28 days apart

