The study will progress from Cohort 1 to Cohort 2, and from Cohort 2 to Cohort 3 when the cumulative safety data of the previous cohort up to Day 8 have been collected and, reviewed by the SRC, and who will provide authorisation to proceed to the next dose cohort by the process described in Section 7.1. Vaccination for Cohorts 4, 5 and 6 will be initiated only once the SRC have completed their review of the aggregated safety and tolerability data from Cohorts 1, 2 and 3.

Adjustment to the currently outlined subsequent dose level, dosing regimen, and period of subjects' follow-up may be made by the SRC based on data from the prior completed dose level. However, the total dose to be administered in a given cohort will not exceed the one currently outlined in the protocol.

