7.1 Data Review by the Safety Review Committee

The SRC will be responsible for the assessment of available safety and tolerability data for each cohort and to make decisions with regards to study progression through the three cohorts in Part 1 and prior to initiating vaccination for Part 2. The SRC will be composed of at least the PI, one Sponsor representative, and a Syneos Health Medical Monitor. Additional non-voting members of the SRC may also be included in the SRC to contribute to discussions, but will not have a vote in the decision to progress to a new cohort. The conduct of the SRC during the study will be as dictated in the SRC Charter.

In Part 1, for the purpose of progressing from sentinels to dosing the rest of cohort (ROC), an informal SRC discussion will be held after the sentinel's safety data are available for 48-hours post dose (Day 2). If no AEs of note, SAEs, or severe AEs, dosing of the ROC may be conducted

without a formal SRC meeting, and dosing may commence with email confirmation from the SRC members (this process will be repeated again following administration of the second dose).

For the purpose of progressing from Cohort 1 to Cohort 2 and from Cohort 2 to Cohort 3, a formal SRC meeting will be held after aggregated safety and tolerability data up to at least Day 8 (7 days post-first dose) are available for all eligible subjects from each cohort before proceeding with vaccination of the next cohort (and similarly up to at least Day 36 following the second vaccination dose at Day 29). As the maximal immunological response is not expected to be reached by Day 8, immunological data will not be assessed as part of the SRC decision making process.

The potential decisions of the SRC are:

1. Escalate to the next planned dose level; or
2. Suspend dose escalation until further review of study data can be made, allowing the SRC to determine whether predefined halting rules have been met. Dose escalation may resume once the SRC concludes that no halting rules have been met; or
3. Stop dose escalation;
4. Terminate the study.

The SRC will conduct a blinded review of the data; however the blind may be broken for individual subjects if judged necessary, prior to making a decision on dose escalation. Dose escalation may occur only following mutual agreement between the SRC members. Decisions taken by the SRC will be documented and submitted to the HREC overseeing the study, along with supportive data.

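### Section 7.2 writes no automatic hold for a higher-dose cohort that is already open and still being dosed when a halting rule is met at a lower dose

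*Protocol*

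**What the plan says.** Section 7.2 introduces its rules as "pre-defined criteria that halt the conduct of the study (either a single cohort or the entire study", the last words being the close of a parenthesis. Before the listed triggers it says: "The following events will result in a temporary halt of dosing within that cohort". After the list, dosing is suspended for everyone in the affected cohort, and "continuation of other cohorts at lower or equivalent dose levels will be evaluated on a case-by-case basis". The SRC then reviews the event, and dosing of the cohort may resume if the SRC finds that no rule was in fact met. No criterion for halting the entire study follows the opening sentence.

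For doses not yet opened there is a separate control. Section 7.1: "Dose escalation may occur only following mutual agreement between the SRC members". Section 5.2.2 has the safety of the 5 mcg dose "evaluated by a Safety Review Committee prior to escalation to the 15 mcg, and similarly prior to escalation to the 45 mcg dose".

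On sequence, Section 6.1 opens the next Part 1 cohort "when the cumulative safety data of the previous cohort up to Day 8 have been collected and, reviewed by the SRC". For older adults the same section says: "Vaccination for Cohorts 4, 5 and 6 will be initiated only once the SRC have completed their review". Section 6 gives Cohorts 4 to 6 no sentinels. On the size of Cohort 3, Section 6 states that "24 subjects will receive Treatment C, and 24 subjects will receive Treatment D".

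**The concern.** The rule covers the affected cohort (suspended) and cohorts at the same or a lower dose (considered individually). It leaves out cohorts at a higher dose, where a dose-related harm would matter most. If a possibly related serious adverse event occurs at 5 mcg while 15 or 45 mcg is being given, the site has a written instruction for the 5 mcg cohort and none for the others.

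This is a first-in-human trial of a novel antigen. Pre-defined halting rules are meant to act before anyone deliberates. If the hold on the higher dose has to be inferred or decided on the day, the rule does not do that for the cohorts concerned. In Part 2 the people concerned are 56 or older and are dosed without sentinels.

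**Working it through.** **Inputs**
- Active first injections (Sections 6 and 8.2): 24 in each of Cohorts 1, 2, 4, 5 and 6. Cohort 3 has 24 (Treatment C) + 24 (Treatment D) = 48, because both arms receive 45 mcg at the first dose. Placebo: 8 per cohort.
- Dose: 5 mcg in Cohorts 1 and 4, 15 mcg in Cohorts 2 and 5, 45 mcg in Cohorts 3 and 6.
- Sentinels (Section 6): two in each Part 1 cohort. For Cohort 3 the text gives 1 active and 1 placebo. For Cohort 2 it does not give the split, so 1 active is assumed. Part 2 has none.
- Sentinel release (Section 7.1): the rest of a Part 1 cohort is dosed only after SRC confirmation on the sentinel data.
- Visit windows (Section 4): Day 8 ±1, Day 29 ±2.

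**Check against the stated sample size**

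32 + 32 + 56 + 32 + 32 + 32 = 216, as in Section 8.2. Active: 5 × 24 + 48 = 168. Placebo: 6 × 8 = 48. Sum: 168 + 48 = 216.

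**Can the overlap happen?**

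The next Part 1 cohort may open on Day 8 data, and the lower cohort's second dose is on Day 29. The gap is 29 − 8 = 21 days. With the windows it runs from 27 − 9 = 18 to 31 − 7 = 24 days, if the review uses a Day 8 cut. Adverse events are collected to Day 394 (Section 9.15.2). A trigger in a lower cohort after its Day 8 review can therefore coincide with first doses in the next cohort. This follows from the stated sequence alone.

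**How many injections?**

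Outstanding = sum, over open cohorts at a higher dose than the cohort with the event, of (active first injections − those already given).

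| Situation | Active first injections with no written hold |
|---|---|
| Event in Cohort 1, Cohort 2 just opened | 1 (active sentinel, assumed); the rest need SRC release |
| Event in Cohort 1, Cohort 2 released | at most 24 − 1 = 23 (22 to 24 if the pair held 2 or 0 active) |
| Event in Cohort 1 or 2, Cohort 3 just opened | 1 (active sentinel); the rest need SRC release |
| Event in Cohort 1 or 2, Cohort 3 released | at most 48 − 1 = 47 |
| Event in Cohort 4, Part 2 parallel | (24 + 24) × (1 − x) |
| Event in Cohort 5, Part 2 parallel | 24 × (1 − x) |
| Part 2 staged, higher cohort not yet opened | 0 |
| Part 2 staged, late event while one higher cohort is being dosed | at most 24 |
| Event at 45 mcg, or first dosing finished | 0 |

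Here x is the fraction of the higher-dose Part 2 cohorts already dosed, which is an assumption. For a Cohort 4 event, x = 0.25, 0.50, 0.75 and 1 give 36, 24, 12 and 0. The value 48 needs x = 0, which hardly fits parallel dosing.

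The Cohort 3 and Part 2 figures do not add. The Synopsis starts Part 2 only after all Part 1 subjects have had their first vaccination. Second doses are left out because they have their own SRC reviews (Synopsis; Sections 6 and 7.1).

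**With the fix**, every figure in the right-hand column becomes 0, because open higher-dose cohorts are held until the SRC has reviewed the event.

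**The case against.** The best reply is that the sentence already implies the answer. It contemplates continuation only at the same or a lower dose, and it would be odd for safer doses to need evaluation while higher ones ran on. This reading is plausible. It is not written, however: the limit to the affected cohort describes the whole of the mandatory action, and a reader at the site cannot tell implied suspension from silence.

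Other controls exist. One SRC option in Section 7.1 is to suspend escalation while it determines whether a halting rule has been met. Section 7.2 makes SRC review follow a halt, contains a general clause on a toxicity pattern seen in more than one person, and lets the sponsor discontinue the study. Section 9.7 requires a physician to judge each vaccination appropriate. Serious events are reported within 24 hours (Section 9.15.3), the trial has one site, and the principal investigator sits on the SRC. All this makes long uncontrolled dosing unlikely. None of it is an automatic hold on a higher-dose cohort already open. The general clause, too, halts dosing of a cohort and does not say that a higher-dose one must stop.

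The sentinel step also stands as an objection to any count that takes the full size of a newly opened Part 1 cohort. The ceilings above allow for it.

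The SRC charter is not shown and may contain a cross-cohort hold. Section 7.2 nevertheless states an action for other cohorts itself, and that statement is incomplete.

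**Conclusion.** The gap is in the text: no automatic hold is written for a higher-dose cohort already open and still being dosed. In Part 1 it can affect up to 47 active first injections in Cohort 3, or about 23 in Cohort 2 if one of its sentinels is active. Both figures apply only after sentinel release. In Part 2 the number is below 48 in practice, and only if Cohorts 4 to 6 are dosed in parallel. Their opening together on one SRC review suggests this, but Section 6 calls Part 2 ascending and Figure 1 is not available.

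A reader might infer three stronger things that the documents do not support:
- That 47 or 48 people would be injected after a halt. These are ceilings on what is outstanding. The judgement-based controls would probably act well before they were reached, and the protocol gives no basis for estimating the actual number.
- That the plan lets a new, higher dose be opened after a halt. Sections 5.2.2 and 7.1 require SRC agreement for that.
- That the plan directs higher-dose cohorts to continue. It is silent on them.

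This is a cheap improvement to patient safety.

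**What to change.** In Section 7.2, replace the suspension sentence with wording such as:

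> If any halting rule is met, dosing will be suspended in that cohort and in all open cohorts at higher dose levels, in both Parts, until the SRC has reviewed the event.

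Keep the existing provision that cohorts at the same or a lower dose are considered case by case. In the resumption sentence, refer to the suspended cohorts in place of the single cohort. Add a matching line to the SRC charter.

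The cost is two sentences and the charter line, plus short pauses in higher-dose cohorts. At most, a halt in Cohort 4 would pause Cohort 4 and Cohorts 2, 3, 5 and 6, which is five of six, if all still had doses to give. Some second doses could then fall outside the ±2 day window around Day 29.

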8.1 Rationale for the Study Population

A healthy volunteer population has been selected for Part 1 of the study because healthy subjects with no clinically significant acute or chronic diseases or conditions represent a homogenous population allowing for proper evaluation of the safety and tolerability of a vaccine while minimising the impact of additional confounding factors. No reproductive studies in animals have been conducted with the study vaccine (SARS-CoV-2 Sclamp vaccine) so far. Since the risks to a developing human foetus, or a nursing infant, following exposure to SARS-CoV-2 Sclamp vaccine are unknown at this time, only males and non-pregnant, non-lactating females will be enrolled in this study. Female subjects of childbearing potential and non-surgically-sterile male subjects with female partners of childbearing potential will be required to use a double contraceptive method for the duration of the study and for 90 days following the last administration of the study treatment. A serum pregnancy test will be performed at screening for all women of child bearing potential, and urine pregnancy tests will also be performed prior to each dosing to confirm non-pregnant status.

A healthy older adult population has been selected for Part 2 of the study because older adults have been identified to be at greatest risk of severe disease, hospitalisation and death from COVID-19 (with risk increasing continuously from 60-years of age, and much higher over 70-years). However, it is important that these older adults have no medical co-morbidities associated with an increased risk of severe COVID-19. The ability to induce a robust immune response declines with age, therefore it is important to understand the profile of the immune response between young healthy and older adult populations to evaluate the immunogenicity of the doses tested for the vaccine. The inclusion of a healthy older adult population will enable a comparison of the preliminary immunogenicity and safety characteristics between the two age groups in the study to inform the selection of dose, prior to progression of further clinical development of the vaccine.

As the study will not be assessing pharmacokinetic parameters, there is no anticipated impact of including smokers in the population, and smoker status is considered unlikely to impact the aims of the study. It is recognised, however that smokers tend to have higher rates of respiratory and

cardiovascular issues, as well as a higher chance of contracting lung and chest infections. The inclusion of smokers in the study will therefore, be limited only to social smokers, defined as those who smoke the equivalent of no more than 10 cigarettes per week. Ex-heavy smokers (heavy smoking defined as the equivalent of 25 or more cigarettes per day) may be admitted to the study if they have quit, or reduced their cigarette intake to the defined level of social smoking, for a period of at least 12 months. Further, smokers will be required to abstain from smoking for a minimum of 2 hours prior to each visit to the clinical site, and for at least 4 hours post each study treatment administration.

8.2 Sample Size

It is planned to enroll approximately 216 male and female volunteers for participation in this study.

This study will consist of 6 cohorts (2 cohorts of a lower dose, 2 cohorts of an intermediate dose and 2 cohorts of a higher dose, examining both a single and two dose vaccination regimen). Cohort 1 will include 32 subjects (8 receiving placebo and 24 subjects receiving a low-dose of SARS-CoV-2 Sclamp vaccine administered in a two dose regimen 28 days apart).

Cohort 2 will include 32 subjects (8 receiving placebo and 24 subjects receiving an intermediate dose of SARS-CoV-2 Sclamp vaccine administered in a two dose regimen 28 days apart).

Cohort 3 will include 56 subjects (8 subjects receiving placebo, 24 subjects receiving a higher dose of SARS-CoV2 Sclamp vaccine administered in a two dose regimen 28 days apart, and 24 subjects receiving a single dose of the high-dose of SARS-CoV-2 Sclamp vaccine dosed once followed by placebo 28 days later).

Cohort 4 will include 32 subjects (8 receiving placebo and 24 subjects receiving a lower dose of SARS-CoV-2 Sclamp vaccine administered in a two dose regimen 28 days apart).

Cohort 5 will include 32 subjects (8 receiving placebo and 24 subjects receiving an intermediate dose of SARS-CoV-2 Sclamp vaccine administered in a two dose regimen 28 days apart).

Cohort 6 will include 32 subjects (8 subjects receiving placebo, 24 subjects receiving a higher dose of SARS-CoV-2 Sclamp vaccine administered in a two dose regimen 28 days apart).

No prospective calculations of statistical power have been made. The sample size of 24 subjects per treatment group has been selected to provide information on safety and estimates related to the primary and secondary endpoints.

8.3 Inclusion Criteria

Subjects enrolled in this study will be members of the community at large. The recruitment advertisements may use various media types (e.g., radio, newspaper, the clinical site Web site and volunteer database).

Part 1 Subjects must meet all of the following criteria to be included in the study:

1. Healthy male or non-pregnant female, ≥ 18 and ≤ 55 years of age, with BMI > 18 and < 34.0 kg/m² and body weight ≥ 50.0 kg for males and ≥ 45.0 kg for females.
2. Healthy as defined by:
 - a. The absence of clinically significant illness and surgery within 28 days prior to dosing. Subjects displaying signs or symptoms of an acute and/or febrile illness within 24 hours pre-dose (with at least 3 symptom-free pre-dose days required) will be carefully evaluated for upcoming illness/disease. Inclusion pre-dosing is at the discretion of the Investigator, and the subject may have their scheduled dosing postponed until the condition resolves.
 - b. The absence of clinically significant history of neurological, endocrine, cardiovascular, respiratory, haematological, immunological, psychiatric, gastrointestinal, renal, hepatic, and metabolic disease.
3. Non-smokers or social smokers (defined as the equivalent of fewer than 10 cigarettes per week). Ex-heavy smokers (heavy smoking defined as the equivalent of 25 or more cigarettes per day) may be admitted if they have quit, or reduced their cigarette intake to the defined level of social smoking, for a period of at least 12 months.
4. Women of childbearing potential (WOCBP) or men whose sexual partners are WOCBP must be able and willing to use at least 2 highly effective methods of contraception commencing at enrolment, during the study and for 3 months after last treatment administration. A female subject is considered to be a WOCBP following menarche and until she is in a post-menopausal state for 12 consecutive months (without an alternative medical cause) or otherwise permanently sterile (for which acceptable methods include hysterectomy, bilateral salpingectomy, and bilateral oophorectomy). A follicle-stimulating hormone (FSH) test may be used to confirm post-menopausal state. Examples of acceptable methods of contraceptive methods (for female subjects) to be used throughout the study include:
 - a. Simultaneous use of hormonal contraceptives, started at least 28 days prior to first study treatment administration and must agree to use the same hormonal contraceptive throughout the study, and condom for the male partner;
 - b. Simultaneous use of intra-uterine contraceptive device, placed at least 28 days prior to first study treatment administration, and condom for the male partner;
 - c. Simultaneous use of diaphragm or cervical cap and male condom for the male partner, started at least 28 days prior to first study treatment administration;
 - d. Sterile male partner (vasectomized since at least 6 months prior to first study treatment administration);
 - e. True abstinence, defined as no sexual intercourse with a male partner, (for heterosexual couples) for at least 28 days prior to first study treatment administration and for at least the duration of the study. Periodic abstinence and withdrawal are not acceptable methods.

5. WOCBP must have a negative urine pregnancy test prior to receiving each dose.
6. Male subjects (including men who have had a vasectomy) with a pregnant partner, a female partner not of childbearing potential, or a same sex partner, must agree to use a condom from the first study treatment administration until at least 90 days after the last study treatment administration.
7. Male subjects must be willing not to donate sperm until 90 days following the last study treatment administration.
8. Must be able to attend all visits for the duration of the study and to comply with all study procedures according to the study schedule.
9. Capable of, and have given, written informed consent.

Part 2 Subjects must meet all of the following criteria to be included in the study:

1. Healthy male or non-pregnant female, ≥ 56 years of age, with BMI >18 and <34.0 kg/m² and body weight ≥ 50.0 kg for males and ≥ 45.0 kg for females.
2. Healthy as defined by:
 - a. The absence of clinically significant illness and surgery within 28 days prior to dosing. Subjects displaying signs or symptoms of an acute and/or febrile illness within 24 hours pre-dose (with at least 3 symptom-free pre-dose days required) will be carefully evaluated for upcoming illness/disease. Inclusion pre-dosing is at the discretion of the Investigator, and the subject may have their scheduled dosing postponed until the condition resolves.
 - b. The absence of clinically significant history of a pre-existing medical condition that is not stable (neurological, endocrine, cardiovascular, respiratory, haematological, immunological, psychiatric, gastrointestinal, renal, hepatic, and metabolic disease). A stable medical condition is defined as disease not requiring significant change in therapy or hospitalization for worsening disease during the 3 months before enrolment.
3. Non-smokers or social smokers (defined as the equivalent of fewer than 10 cigarettes per week). Ex-heavy smokers (heavy smoking defined as the equivalent of 25 or more cigarettes per day) may be admitted if they have quit, or reduced their cigarette intake to the defined level of social smoking, for a period of at least 12 months.
4. Women of childbearing potential (WOCBP) or men whose sexual partners are WOCBP must be able and willing to use at least 2 highly effective methods of contraception commencing at enrolment, during the study and for 3 months after last treatment administration. A female subject is considered to be a WOCBP following menarche and until she is in a post-menopausal state for 12 consecutive months (without an alternative medical cause) or otherwise permanently sterile (for which acceptable methods include hysterectomy, bilateral salpingectomy, and bilateral oophorectomy). A follicle-stimulating

hormone (FSH) test may be used to confirm post-menopausal state. Examples of acceptable methods of contraceptive methods (for female subjects) to be used throughout the study include:

- a. Simultaneous use of hormonal contraceptives, started at least 28 days prior to first study treatment administration and must agree to use the same hormonal contraceptive throughout the study, and condom for the male partner;
 - b. Simultaneous use of intra-uterine contraceptive device, placed at least 28 days prior to first study treatment administration, and condom for the male partner;
 - c. Simultaneous use of diaphragm or cervical cap and male condom for the male partner, started at least 28 days prior to first study treatment administration;
 - d. Sterile male partner (vasectomized since at least 6 months prior to first study treatment administration);
 - e. True abstinence, defined as no sexual intercourse with a male partner, (for heterosexual couples) for at least 28 days prior to first study treatment administration and for at least the duration of the study. Periodic abstinence and withdrawal are not acceptable methods.
5. WOCBP must have a negative urine pregnancy test prior to receiving each dose.
 6. Male subjects (including men who have had a vasectomy) with a pregnant partner, a female partner not of childbearing potential, or a same sex partner, must agree to use a condom from the first study treatment administration until at least 90 days after the last study treatment administration.
 7. Male subjects must be willing not to donate sperm until 90 days following the last study treatment administration.
 8. Must be able to attend all visits for the duration of the study and to comply with all study procedures according to the study schedule.
 9. Capable of, and have given, written informed consent.

